## 12.2.2 Display of Adverse Events

Table 12.2.2.1 Summary of AEs.

Category	N	%
Patients with at least one AE regardless relationship		
Any treatment-related AE		
Any grade 3/4 AE		
Any grade 3/4 treatment-related AE		
Any SAE in DB		
Any treatment-related SAE		
Any grade 3/4 SAE		
Any grade 3/4 treatment-related SAE		
AEs leading to death		
AEs treatment-related leading to death		
AEs leading to dose delay		
AEs leading to dose reduction		
AEs leading to treatment discontinuation		
AEs treatment-related leading to treatment discontinuation		

Table 12.2.2.2 Treatment-related AEs. Worst grade by patient

SOC	Preferred Term	Grade 1		...	Grade 4		All*	
		N	%		N	%	N	%
Blood and lymphatic system disorders	Anemia NOS							
	...							
	...							
Cardiac disorders	Arrhythmia NOS							
	...							

(\*) Any grade

Table 12.2.2.3 Treatment-related AEs. Worst grade by cycle

SOC	Preferred Term	Grade 1		...	Grade 4		All*	
		N	%		N	%	N	%
Blood and lymphatic system disorders	Anemia NOS							
	...							
	...							
Cardiac disorders	Arrhythmia NOS							
	...							

\* Any grade

Table 12.2.2.4 Adverse Events regardless of relationship. Worst grade by patient

SOC	Preferred Term	Grade 1		...	Grade 4		All*	
		N	%		N	%	N	%
Blood and lymphatic system disorders	Anemia NOS							
	...							
	...							
Cardiac disorders	Arrhythmia NOS							
	...							

(\*) Any grade

Table 12.2.2.5 Adverse Events regardless of relationship. Worst grade by cycle

SOC	Preferred Term	Grade 1		...	Grade 4		All*	
		N	%		N	%	N	%
Blood and lymphatic system disorders	Anemia NOS							
	...							
	...							
Cardiac disorders	Arrhythmia NOS							
	...							

(\*) Any grade

Listing 12.2.2.6 Treatment-related grade 3-4 AEs. Worst grade per patient

Patient id.	SOC Name	Preferred term	Grade

Listing 12.2.2.7 Treatment-related grade 3-4 AEs. Worst grade by cycle

Patient id.	Cycle	SOC Name	Preferred term	Grade

Listing 12.2.2.8 Adverse Events grade 3-4 regardless of relationship. Worst grade per patient

Patient id.	SOC Name	Preferred term	Grade

Listing 12.2.2.9 Adverse Events grade 3-4 regardless of relationship. Worst grade by cycle

Patient id.	Cycle	SOC Name	Preferred term	Grade

Table 12.2.2.10 Treatment-related SAEs. Worst grade by patient

SOC	Preferred Term	Grade 1		...	Grade 4		All*	
		N	%		N	%	N	%
Blood and lymphatic system disorders	Anemia NOS							
	...							
	...							
Cardiac disorders	Arrhythmia NOS							
	...							

(\*) Any grade

Table 12.2.2.11 Treatment-related SAEs. Worst grade by cycle

SOC	Preferred Term	Grade 1		...	Grade 4		All*	
		N	%		N	%	N	%
Blood and lymphatic system disorders	Anemia NOS							
	...							

	...						
Cardiac disorders	Arrhythmia NOS						
	...						

\* Any grade

Table 12.2.2.12 SAEs regardless of relationship. Worst grade by patient

SOC	Preferred Term	Grade 1		...	Grade 4		All*	
		N	%		N	%	N	%
Blood and lymphatic system disorders	Anemia NOS							
	...							
	...							
	...							
Cardiac disorders	Arrhythmia NOS							
	...							

(\*) Any grade

Table 12.2.2.13 SAEs regardless of relationship. Worst grade by cycle

(\*) Any grade

At the time of the analysis, if appropriate, grouping of similar or clinically related items will be made.

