### 7.1.1 *Toxicity and Adverse Events*

All the adverse events will be coded using the Medical Dictionary for Regulatory Activities (MedDRA).

The toxicity evaluation will be coded with the National Cancer Institute Common Terminology Criteria for Adverse Events (NCI-CTCAE), version 4.

As far as all the toxicities are concerned, the NCI-CTCAE grade will be used wherever an NCI-CTCAE grading exists. Otherwise, the severity will be noted. As a convention, the term «Grade» will always be used. Toxicities will be described according to the worst NCI-CTCAE grade or, for toxicities which do not form the subject of NCI-CTCAE classification, according to the worst severity.

Summary of overall AEs will be done by System Organ Class (SOC) and Preferred Term (PT), by severity (worst toxicity grade), by relationship to the study drug and by AE outcome. Tables will be sorted by SOC/PT coded with MedDRA.

A frequency table will be made for the AEs leading to cycle delay, dose reduction or withdrawal of study medication. Adverse events with outcome of death will also be presented by relationship to the study drugs.

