### 12.3.2 Deaths

Table 12.3.2.1 Cause of death

Reason*	N	%
Malignant disease		
Study drug related adverse event		
Non-study drug related AE		
Other		
Total		

(\*) Denominator=Number of patients who died

Listing 12.3.2.2 Deaths

Patient id.	Death date	Cause	Comments	Autopsy	Number of cycles administered	Last infusion date	Time on treatment*	Time from Last dose**

(\*) Time on treatment: defined as last infusion date plus 30 days, or date of death or subsequent therapy (whichever comes first) minus first infusion date. (\*\*Time from last dose defined as death date minus last infusion date.

Listing 12.3.2.3 AEs with outcome death

Patient id.	Cycle	Preferred term code	Adverse event reported (verbatim)	Grade	Relationship	Onset date	Date of death	Action

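### The adverse-event severity tables stop at grade 4, so a fatal event has no severity column, including in the required comparison by starting dose and cohort

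*SAP*

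**What the plan says.** The governing rule is in SAP 7.1.1: "Toxicities will be described according to the worst NCI-CTCAE grade". SAP 12.2.1 repeats it. The scale is NCI-CTCAE version 4.

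The shells in SAP 12.2.2 apply the rule as follows:

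- **Worst-grade tables.** Tables 12.2.2.2 to 12.2.2.5 (AEs) and 12.2.2.10 to 12.2.2.12 (SAEs) have columns from grade 1 to grade 4, then an All column footnoted as covering every grade. The header of Table 12.2.2.13 is not legible in the text available, so it is not counted here.
- **Summary table.** Table 12.2.2.1 has the rows "Any grade 3/4 AE" and "Any grade 3/4 treatment-related AE", with matching SAE rows. It has no row for grade 3 or higher. Further down are the separate rows "AEs leading to death" and "AEs treatment-related leading to death".
- **Listings.** Listings 12.2.2.6 to 12.2.2.9 are limited to grade 3-4, for example "Treatment-related grade 3-4 AEs. Worst grade per patient" and "Listing 12.2.2.8 Adverse Events grade 3-4 regardless of relationship. Worst grade per patient".

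Deaths are also shown in Tables 10.2.1, 10.2.3 and 10.2.5 (discontinuation reasons), Table 12.3.2.1 (cause of death), Listing 12.3.2.2 and Listing 12.3.2.3 ("AEs with outcome death"), which has a grade field.

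For the AE analysis by starting dose and cohort, SAP 12.2.1 requires four tables: 12.2.2.2, 12.2.2.3, 12.2.2.4 and 12.2.2.5.

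**The concern.** A table that claims to show the worst grade should have a place for the worst grade possible. Here the highest severity column is grade 4. Fatal events can be expected in these tables: Protocol 11.1.2.1 asks sites to record the cause of death as the SAE term, so a fatal event arrives under its own preferred term. Fatal disease progression does not, because Protocol 11.2.2 exempts it from SAE reporting.

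What is at stake is the reading of severe toxicity by starting dose. The starting dose changed during the trial from 7 mg flat to 3.5 mg/m², and the SAP asks for AE tables split on that change. If the graded columns leave out fatal events and no death table is required beside them, the two dose groups are compared on severity without the most severe outcome in view.

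**Working it through.** The plan states no figure on this point, so there is nothing to reproduce. The check is to trace one fatal event through the shells, then bound the effect on the summary rows.

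**Assumption.** A fatal AE carries grade 5. The documents name NCI-CTCAE v4 but do not reproduce its scale.

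**Step 1: tables by preferred term.** For one preferred term, All = G1 + G2 + G3 + G4 + G5, where each term counts patients by worst grade. The shell prints All and G1 to G4. A patient whose worst grade for that term is 5 is therefore in All and in no graded column. A reader can recover her only as G5 = All − (G1 + G2 + G3 + G4). This loss is certain under the assumption.

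**Step 2: grade 3-4 listings.** The same event falls outside Listings 12.2.2.6 to 12.2.2.9 by their titles. This too is certain.

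**Step 3: summary rows.** The rows in Table 12.2.2.1 say any grade 3/4 event. Let d be the number of patients with a fatal AE, q the share of them with another grade 3/4 AE, and N the number of patients in the denominator.

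- Programmed as any event of that grade: shortfall = d(1 − q)/N.
- Programmed from each patient's single worst grade: shortfall = d/N, whatever q is.

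The SAP does not say which applies. With d = 2 and N = 110, the first formula gives 1.8 percentage points at q = 0, 1.1 at q = 0.4, 0.4 at q = 0.8 and 0 at q = 1.

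**Step 4: range.** The documents give no number of fatal AEs, so d is assumed to be 1, 2 or 3. Values of N: 20 (Cohort A1), 30 (the window of the stopping rule in Protocol 8.3.3), 53 (Cohort A minimum), about 110 (expected total, SAP 5.1), and 137 = 53 + 20 + 64 (sum of the cohort targets). The largest shortfall, 100 × d/N in percentage points, is:

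| d | N = 20 | N = 30 | N = 53 | N = 110 | N = 137 |
|---|---|---|---|---|---|
| 1 | 5.0 | 3.3 | 1.9 | 0.9 | 0.7 |
| 2 | 10.0 | 6.7 | 3.8 | 1.8 | 1.5 |
| 3 | 15.0 | 10.0 | 5.7 | 2.7 | 2.2 |

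If the rows count any event, the smallest shortfall is 0 in every cell. These N are evaluable patients, whereas the safety set is all treated patients (SAP 4.3). Its size is not given. Every evaluable patient was treated, so the safety denominator is at least as large and the shortfall no larger.

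**Step 5: do the death outputs cover the dose comparison?** The required starting-dose outputs are:

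- exposure tables (SAP 12.1)
- Tables 12.2.2.2 to 12.2.2.5 (SAP 12.2.1)
- laboratory tables (SAP 12.4)
- transfusions and G-CSF (Table 12.6.5)

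None reports deaths. SAP 12.2.1 allows further splits by initial dose at discretion. Appendix I displays outputs by cohort and/or total, but Cohort A appears at both doses in the group list of SAP 12.2.1, so a cohort split does not separate the doses there. Listings 12.3.2.2 and 12.3.2.3 have no starting-dose field.

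**The case against.** The strongest reply is that fatal toxicity is already well reported. Table 12.2.2.1 carries its own death rows, SAP 7.1.1 presents fatal AEs by relationship to study drug, the discontinuation tables have toxic-death rows, and Listing 12.3.2.3 shows each fatal AE with its grade. The all-grades column keeps the event in its total. Showing grade 3/4 and fatal events as separate categories is a legitimate display, and a row labelled grade 3/4 that counts grade 3/4 is not wrong. All of this stands. A reader might infer that deaths vanish from the safety report, or that the severity percentages are in error. The documents support neither.

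A reader might also infer that the headline severe-event rates will make a dose with more toxic deaths look milder. That goes too far: Table 12.2.2.1, which holds those rows, is not on the required starting-dose list, and a patient with any other grade 3/4 event may still be counted. The point about the dose comparison rests only on the graded columns of Tables 12.2.2.2 to 12.2.2.5.

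The numbers are also open to challenge. The deaths are assumed, and three in a 20-patient cohort has no basis in the documents. The first-in-human study described in Protocol 1.2.1.2 had no treatment-related deaths. The percentages are therefore bounds, not forecasts.

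Finally, if the database capped the grade at 4 and recorded death only as an outcome, the gap would not arise. The SAP would then need to say so.

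Could the shells be mere templates, with a grade 5 column added when needed? The dots lie between grades 1 and 4, so they do not stand for grade 5. The on-treatment coagulation shells stop at grade 3, which suggests that the top grade was chosen table by table. That is only weak evidence, since the baseline coagulation shell runs to grade 4.

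**Conclusion.** The point holds as a display gap of modest weight. Given grade 5 for fatal AEs, the loss from the graded preferred-term columns and the grade 3-4 listings is certain. The loss from the patient-level summary rows is conditional. For an assumed 1 to 3 deaths it is 0 to 2.7 points with about 110 patients and 0 to 15 points in a 20-patient cohort. At the protocol's own stopping threshold of two related deaths in 30 patients it is 0 to 6.7 points.

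The part that the rest of the plan does not repair is the required comparison by starting dose and cohort, where the severity columns omit fatal events and no death output is required alongside. Response rate, sample size and error rates are untouched. The safety stopping rule counts treatment-related deaths directly, so it is unaffected too.

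**What to change.** - Add a grade 5 column to Tables 12.2.2.2 to 12.2.2.5 and 12.2.2.10 to 12.2.2.13. This also puts fatal events into the required comparison by starting dose and cohort.
- Add grade 3-or-higher rows to Table 12.2.2.1 for AEs and SAEs, overall and treatment-related. Define them as at least one event of that grade. Keep the existing grade 3/4 and death rows, so that the non-fatal count is not lost.
- Extend Listings 12.2.2.6 to 12.2.2.9 to grade 3-5.
- State in SAP 7.1.1 that a fatal AE is graded 5 or, if the database records death only as an outcome, how such an event is placed in the severity columns.

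The cost is a small change to shells and programs.

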### **12.2.3 Evolution of signs and symptoms during the treatment**

Worst grade signs and symptoms present during treatment and at baseline regardless of relationship will be shown

Table 12 2 3 1 Shift of signs and symptoms during the treatment

### 12.3 Serious Adverse Events and Deaths.

### 12.3.1 Serious Adverse Events

### Listing 12.3.1.1 SAEs

The Pharmacovigilance Department will provide the narratives of the SAEs from the Pharmacovigilance Database (DB).

### 12.3.2 Deaths

Table 12.3.2.1 Cause of death

Reason*	N	%
Malignant disease		
Study drug related adverse event		
Non-study drug related AE		
Other		
Total		

(\*) Denominator=Number of patients who died

Listing 12.3.2.2 Deaths

Patient id.	Death date	Cause	Comments	Autopsy	Number of cycles administered	Last infusion date	Time on treatment*	Time from Last dose**

(\*) Time on treatment: defined as last infusion date plus 30 days, or date of death or subsequent therapy (whichever comes first) minus first infusion date. (\*\*Time from last dose defined as death date minus last infusion date.

Listing 12.3.2.3 AEs with outcome death

Patient id.	Cycle	Preferred term code	Adverse event reported (verbatim)	Grade	Relationship	Onset date	Date of death	Action

### 12.4 Clinical Laboratory Evaluation

Subgroup analysis will be performed according to starting dose (7 mg FD vs. 3.5 mg/m^2) and Cohort.

The groups will include:

- Patient treated at 7 mg FD Cohort B
- Patient treated at 7 mg FD Cohort A
- Patient treated at 7 mg FD any Cohort
- Patient treated at 3.5 mg/m^2 Cohort A
- Patient treated at 3.5 mg/m^2 Cohort A1
- Patient treated at 3.5 mg/m^2 any Cohort

The tables will be annotated by adding a letter as suffix.

The tables included in the subgroup analysis are the following:

Table 12.4.1.1 Hematological abnormalities during treatment, worst grade per patient

Table 12.4.1.2 Hematological abnormalities during treatment, worst grade per cycle

Table 12.4.2.1 Biochemical abnormalities during treatment, worst grade per patient

Table 12.4.2.2 Biochemical abnormalities during treatment, worst grade per cycle

Table 12.4.3.1 Coagulation abnormalities during treatment, worst grade per patient

Table 12.4.3.2 Coagulation abnormalities during treatment, worst grade per cycle

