5.2.3. Dose Reduction

Study treatment may continue with an appropriate dose reduction ([Table 3](#)) if patient benefit is perceived by the Investigator (upon Sponsors' agreement), even after the patient experienced any of the following:

- Grade ≥ 3 treatment-related non-hematological toxicity. Exceptions are: grade 3 nausea and/or vomiting not optimally treated, grade 3 asthenia lasting < 1 week, grade 3 diarrhea lasting ≤ 2 days or not optimally treated, grade 3-4 hypersensitivity and/or extravasation reactions, grade 3 transient ALT/AST elevations which are rapidly reversible and not leading to subsequent delays, and/or not clinically relevant biochemical abnormalities [i.e., in gamma-glutamyltransferase (GGT), lactate dehydrogenase (LDH) and/or alkaline phosphatase (AP) levels], none of which require dose reduction to be implemented.
- Grade 4 thrombocytopenia or grade 3 thrombocytopenia concomitantly with grade ≥ 3 bleeding.
- Frequent or prolonged (>1 week) dose delays due to treatment-related toxicity.

Patients experiencing grade 4 neutropenia or febrile neutropenia during the preceding cycle, or treatment delays exclusively due to neutropenia that lasted >1 week, may continue treatment without any dose reduction but must receive secondary prophylaxis with G-CSF instead. The G-CSF secondary prophylaxis will be administrated subcutaneously at 300 μ g/day for five consecutive days starting on Day +3 of the corresponding cycle. If despite appropriate G-CSF prophylaxis, grade 4 neutropenia or febrile neutropenia re-occurs, then dose reduction should be implemented.

Table 3. Guidelines for dose reduction.

Dose reduction level*	PM01183 dose (mg, FD) Patients included under protocol versions 1.0, 2.0	PM01183 dose (mg/m ²) Patients included from protocol version 3.0 onward**
1	7.0	3.5
-1	6.0	2.6
-2	5.0	2.0

* Except for grade ≥ 3 nausea and/or vomiting not optimally treated, grade 3 asthenia lasting < 1 week, grade 3 diarrhea lasting ≤ 2 days or not optimally treated, grade 3-4 hypersensitivity and/or extravasation reactions, grade 3 transient ALT/AST elevations which are rapidly reversible and not leading to subsequent delays, and/or isolated not

clinically relevant biochemical abnormalities (i.e., GGT, LDH and/or AP), none of which require dose reduction to be implemented.

**Dose will be capped at BSA of 2.0 m² (starting dose will not exceed 7 mg). BSA will be calculated according to standard practice at each center.

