5.3.3. Prohibited Medications/Therapies

The following medications or therapies are not allowed to be administered during the study:

- Concomitant administration of any other antineoplastic therapy, except therapy with LHRH agonist if applicable.
- Any other investigational agents.
- Immunosuppressive therapies other than corticosteroids.
- Primary G-CSF prophylaxis or treatment of non-febrile grade ≤ 3 neutropenia with G-CSF (unless previously agreed case-by-case between the Investigator and the Sponsor).
- Aprepitant, fosaprepitant and directly related compounds.
- Radiotherapy (RT), except for bone limited-field bone radiation for pain control purposes.

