### **8.9 Subgroup Analysis**

The analysis will be done by Cohort and additionally, if clinically appropriate, the Cohorts might be pooled into one, whenever differences between Cohorts are considered not relevant. In such case, the point estimates and their 95% CIs will be also reassessed in order to obtain more accurate calculations.

Efficacy subgroup analysis will be performed in Cohort A according to prior treatment with platinum (Yes vs. No), BRCA status (BRCA1 vs. BRCA2), hormonal status (Triple negative vs. HR+), number of advanced chemotherapy lines , prior PARPi (Yes vs. No)and starting dose (7 mg FD vs. 3.5 mg/m^2).

Additional efficacy subgroup analysis will be performed in Cohorts A+A1 according to prior PARPi (Yes vs. No). Safety subgroup analysis will be performed according to starting dose (7 mg FD vs. 3.5 mg/m^2), these analysis include laboratory abnormalities and adverse events.

If clinically relevant, other subgroup analysis may be performed in order to explore the activity of PM01183 in specific breast cancer subpopulations.

No differentiation by center is planned.

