#### 12.4.4 Laboratory Values Over Time

In this section, grades 3-4 hematological and liver enzyme abnormalities will be displayed according to the cycle in which they occurred.

Table 12.4.4.1 Evolution of hematological abnormalities from baseline, worst case per patient.

Baseline		Baseline grade*	Worst grade per patient						Total	
			0		1		...			
			N	%	N	%	N	%	N	%
Baseline	Neutropenia	Grade 0								
		Grade 1								
		.....								
	Thrombocytopenia	Grade 0								
		Grade 1								
		.....								
	....	Grade 0								
		Grade 1								
		.....								

\*Defined as the last value recorded before or on the date of first infusion.

Table 12.4.4.2 Evolution of hematological abnormalities from baseline, worst case in the first cycle per patient.

Baseline		Baseline grade*	Worst grade in the first cycle per patient						Total	
			0		1		...			
			N	%	N	%	N	%	N	%
Baseline	Neutropenia	Grade 0								
		Grade 1								
		.....								
	Thrombocytopenia	Grade 0								
		Grade 1								
		.....								
	....	Grade 0								
		Grade 1								
		.....								

\*Defined as the last value recorded before or on the date of first infusion.

Table 12.4.4.3 Evolution of hematological abnormalities from baseline, worst case in the last cycle per patient.

Baseline		Baseline grade*	Worst grade in the last cycle per patient						Total	
			0		1		...			
			N	%	N	%	N	%	N	%
Baseline	Neutropenia	Grade 0								
		Grade 1								
		.....								
	Thrombocytopenia	Grade 0								
		Grade 1								
		.....								
	....	Grade 0								
		Grade 1								
		.....								

\*Defined as the last value recorded before or on the date of first infusion.

Table 12.4.4.4 Evolution of biochemical abnormalities from baseline, worst case per patient.

Baseline		Baseline grade*	Worst grade per patient						Total	
			0		1		...			
			N	%	N	%	N	%	N	%
Baseline	AST increase	Grade 0								
		Grade 1								
		.....								
		ALT increase	Grade 0							
Baseline	ALT increase	Grade 1								
		.....								
		...	Grade 0							
		Grade 1								
		.....								

\*Defined as the last value recorded before or on the date of first infusion.

Table 12.4.4.5 Evolution of biochemical abnormalities from baseline, worst case in the first cycle per patient.

Baseline		Baseline grade*	Worst grade in first cycle per patient						Total	
			0		1		...			
			N	%	N	%	N	%	N	%
Baseline	AST increase	Grade 0								
		Grade 1								
		.....								
		ALT increase	Grade 0							

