**Table 12.6.5 Transfusions and G-CSF by dose**

	7 mg FD		3.5 mg/m 		Total	
	N	%	N	%	N	%
Transfusions						
RBC						
Platelets						
G-CSF						

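### The laboratory comparison by starting dose lists only all-cycle tables; the first-cycle tables already in the SAP should be added to it

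*SAP*

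**What the plan says.** SAP 8.9 commits to the comparison: "Safety subgroup analysis will be performed according to starting dose", and "these analysis include laboratory abnormalities and adverse events". SAP 12.4 repeats it for the laboratory data ("Subgroup analysis will be performed according to starting dose" and cohort) and names six groups: 7 mg in Cohort B, in Cohort A and in any cohort; 3.5 mg/m² in Cohort A, in Cohort A1 and in any cohort. Cohort A is the only cohort listed with both doses.

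SAP 12.4 then names six tables: haematology, biochemistry and coagulation, each as worst grade per patient and worst grade per cycle. The per-cycle haematology entry is "Table 12.4.1.2 Hematological abnormalities during treatment, worst grade per cycle". SAP 12.4.1 states that haematological grades are calculated for all cycles.

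SAP 12.4.4 separately specifies "Table 12.4.4.2 Evolution of hematological abnormalities from baseline, worst case in the first cycle per patient" and its biochemistry counterpart, Table 12.4.4.5. Neither is on the by-dose list.

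Several protocol rules make later cycles differ from the first:

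- Protocol 5.2.3: patients with grade 4 or febrile neutropenia, or a delay of more than one week due only to neutropenia, "may continue treatment without any dose reduction but must receive secondary prophylaxis with G-CSF instead".
- Protocol 5.3.2 allows secondary prophylaxis only after Cycle 1. The item in 5.3.3 that begins "Primary G-CSF prophylaxis or treatment of non-febrile grade" rules out primary prophylaxis unless agreed case by case.
- Protocol 5.2.3 permits up to two dose reductions, and 6.2.1.2 sets no fixed number of cycles.
- Protocol 6.6 (Table 5) schedules blood tests on Days 8 and 15 of Cycle 1. From Cycle 3 the Day 10 draw is limited to patients who, in the preceding cycle, had severe related toxicity, a dose adjustment or G-CSF prophylaxis.

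**The concern.** A comparison of starting doses is clearest where patients actually receive the starting dose under the same conditions. In this trial that is Cycle 1. In later cycles, what a patient receives and when she is sampled both depend on the toxicity she has already had.

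The two kinds of listed table are affected differently. The per-cycle table counts reduced-dose and G-CSF-supported cycles as cycles of the starting dose. If one regimen causes more early neutropenia, more of its later cycles are protected, and its pooled rate moves towards the other regimen's. The conditional Day 10 draw adds a detection effect: patients with earlier toxicity are sampled in the second week of later cycles and the others are not. Protocol 1.2.1.2 puts the phase I neutrophil nadir in that second week, around Day 13. The per-patient table accumulates risk with every cycle given, so a group treated for longer looks worse at the same per-cycle risk.

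At stake is how clearly the report can describe laboratory toxicity under the two starting doses. The primary response analysis is not affected.

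**Working it through.** **1. Is a first-cycle laboratory table by starting dose planned anywhere?** The documents give no rate or sample size for this comparison, so there is no figure to reproduce and the check is of the text.

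| Place | What it gives | Separates starting doses in Cycle 1? |
|---|---|---|
| SAP 12.4 list | Six tables, all during treatment | No, all cycles |
| SAP Tables 12.4.4.2 and 12.4.4.5 | Worst grade in first cycle | Not on the by-dose list |
| SAP Tables 12.4.4.11 to 12.4.4.18 | Time course, with first-cycle blocks | No, both starting doses share one column |
| SAP Appendix I, opening text | Display by cohort and/or total | No dose split |
| SAP 12.2.1, last sentence | Possible split by initial dose | Discretionary, and in the adverse event section |

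Displayed by cohort alone, the first-cycle tables would merge both doses in Cohort A.

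**2. Dose reductions are not parallel.** From Protocol Table 3: 6/7 and 5/7 are reductions of 14.3% and 28.6%; 2.6/3.5 and 2.0/3.5 are reductions of 25.7% and 42.9%. Reduced-dose cycles therefore move away from the starting-dose contrast by different proportions in the two groups.

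**3. Per-cycle table, illustration.** Assumptions, none taken from the documents as a Cycle 1 rate: grade 4 risk p per cycle until a first episode (0.40 against 0.20), risk r per cycle afterwards under G-CSF or reduction (0.05 to 0.20, the same in both groups), and five cycles for everyone.

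Rate in cycle k = (1−p)^(k−1)·p + [1−(1−p)^(k−1)]·r, averaged over k = 1 to 5.

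The average proportion still without an episode is (1 + 0.6 + 0.36 + 0.216 + 0.1296)/5 = 0.461 for p = 0.40, and (1 + 0.8 + 0.64 + 0.512 + 0.4096)/5 = 0.672 for p = 0.20.

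| r | p = 0.40 | p = 0.20 | Gap |
|---|---|---|---|
| 0.05 | 0.461×0.40 + 0.539×0.05 = 0.211 | 0.672×0.20 + 0.328×0.05 = 0.151 | 6.1 points |
| 0.10 | 0.238 | 0.167 | 7.1 points |
| 0.20 | 0.292 | 0.200 | 9.2 points |

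The Cycle 1 gap under the same assumptions is 20 points.

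**4. Per-patient table, same inputs, equal cycle numbers.** Ever grade 4 = 1 − (1−p)^n. For n = 5: 1 − 0.6^5 = 92% against 1 − 0.8^5 = 67%, a gap of 25 points. Protection that starts only after a first episode cannot dilute this table.

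**5. Per-patient table, unequal cycle numbers.** With an identical 20% risk per cycle: 1 − 0.8^3 = 49% after three cycles and 1 − 0.8^6 = 74% after six. With 40% against 20% and three against six cycles: 1 − 0.6^3 = 78% against 74%, so most of the difference disappears.

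**The case against.** The strongest reply is that the listed tables are read together. A reader might infer from the per-cycle dilution that the trial would report the two doses as similar. Step 4 shows otherwise: at equal cycle numbers the per-patient table keeps a wide gap on the same inputs. The dilution therefore belongs to the per-cycle table only. The opposite distortion needs unequal cycle numbers, which are possible but not documented.

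Second, the disturbing factors are visible elsewhere. SAP 12.1 tabulates cycles, dose intensity, delays and reductions by starting dose. Listings 12.4.1.4 and 12.6.4 give grade 3–4 haematological events and G-CSF use by patient and cycle. This stands as context, but none of these outputs gives the first-cycle contrast.

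Third, toxicity over the whole course, with its support and reduction rules, is a legitimate descriptive question. No objective in Protocol 3.2 compares doses, and no test or decision depends on the comparison. This stands, and it is why the first-cycle tables belong beside the all-cycle tables and not in their place.

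Fourth, the G-CSF argument concerns neutrophils. For biochemistry, only reduced doses, cycle numbers and draw days matter. Cycle 1 is not perfectly uniform either: therapeutic G-CSF is allowed (Protocol 5.3.2), laboratory tests have a 3-day window, and grade 3 or worse related events trigger retesting every 48–72 hours.

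Two further readings go beyond the text. The 40% in Protocol 1.2.1.2 is the share of phase I patients at the recommended dose with grade 4 neutropenia; it is not stated to be a Cycle 1 rate, so the 40% in the working is only an assumption. A reader might also extend the criticism to "Table 12.6.5 Transfusions and G-CSF by dose". That shell states no counting unit, and the opening text of SAP Appendix I leaves a cohort split open, so neither a missing cycle denominator nor a missing cohort split is established.

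**Conclusion.** The point holds, as a minor one. SAP 12.4 gives a closed list of all-cycle tables for the laboratory comparison by starting dose and leaves out two first-cycle tables that the SAP already contains. The protocol's G-CSF, dose-reduction and Day 10 sampling rules make the per-cycle haematology table a mixture that depends on earlier toxicity. The per-patient tables depend on the number of cycles received.

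The sizes are illustrations. The per-cycle gap of 6–9 points in place of 20 rests on the assumed risks of 40% and 20%, a common later risk of 5–20%, and five cycles for all. The 49% and 74% rest on an assumed 20% risk and on three against six cycles. The documents support the direction of these effects but not their size, and they do not show that the trial's conclusion on the two doses would change. The groups are non-randomised and were defined by protocol version, so first-cycle tables would remove the later-cycle effects but not differences between the patients.

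**What to change.** Add Tables 12.4.4.2 and 12.4.4.5 to the by-dose list in SAP 12.4, for the same six dose-by-cohort groups, and present them alongside the six tables already listed. Add a sentence noting that Cohort A is the only listed cohort with both starting doses, so the any-cohort columns also reflect differences between cohorts.

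The cost is re-running two existing table shells by group. No new data are needed and patient management does not change.

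The gain has limits. First-cycle tables do not show cumulative toxicity, which the all-cycle tables continue to cover. They do not exclude therapeutic G-CSF in Cycle 1. There is no first-cycle coagulation table to add, and the schedule of assessments has no coagulation draw between screening and Day 1 of Cycle 2.
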